	# in-person / VC encounters between index visit and end of follow-up
	# in-person / VC encounters between index visit and end of follow-up period; was the encounter with the PCP: YN; visit's primary purpose;
encounters	# in-person / VC encounters between index visit and end of follow-up period; was the encounter with the PCP: YN; visit's primary purpose; whether visit was for an urgent need: YN; patient new vs. established
encounters  Provider factors	# in-person / VC encounters between index visit and end of follow-up period; was the encounter with the PCP: YN; visit's primary purpose; whether visit was for an urgent need: YN; patient new vs. established Degree (MD, RN, PA, etc.); Prescribing privileges: YN; # in patient panel
Provider factors Independent vars.	# in-person / VC encounters between index visit and end of follow-up period; was the encounter with the PCP: YN; visit's primary purpose; whether visit was for an urgent need: YN; patient new vs. established Degree (MD, RN, PA, etc.); Prescribing privileges: YN; # in patient panel Description

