### **Intent to Treat Analysis**

Differences in change in outcomes will assessed using multi-level mixed models. Intra-class correlation coefficients will be obtained at the patient, clinic, and CHC organization levels for each outcome showed that much organization-level variance could be attributed to the clinic level. Thus, clustering was accounted for by random effects for clinic and patient, and a fixed effect for organization. Analyses will adjust for fixed effects: distribution of eligible patients by age, race / ethnicity, gender, rural / urban status, and federal poverty level (FPL) at index visit; number of ambulatory visits during the follow-up period; and time from index to last visit. These variables were selected *a priori* and will be confirmed by descriptive analyses, to determine whether there are significant differences between baseline intervention and control organization and patient characteristics. After checking distributions, negative binomial mixed-models or poisson mixed-model will be used for reversible risk analyses, and linear-mixed models for all other outcomes.

Patients diagnosed with diabetes during the follow-up period will be excluded from reversible risk analyses because diabetes might be diagnosed more often with CDSS use. Presence of diabetes raises reversible risk estimations even if CVD risk factor control was addressed; this exclusion will remove the possibility of confounding based on likelihood on new diabetes diagnosis.

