#### **Supplement Addendum**

- (1) Descriptive Analyses (Aim 2a)
  - We will conduct a descriptive analysis on the following process outcomes: (1) Encounter patterns; (2) Rates of missed or cancelled appointments at in-person vs. VC (telephone, video) encounters; (3) Appointment wait times by encounter type, and (4) CV Wizard use (in encounters where there are CV Wizard CDS suggestions by encounter type.
  - We will use standard statistical tests (e.g., chi-square, t-tests) to describe measures in the periods pre- vs. post-COVID's onset.
- (2) Regression Analyses (Aim 2b)
  - Encounter is the unit of analysis.
  - We will assess associations between encounter type and: (1) Action taken on needed care plan components; (2) Up-to-date documentation of BP and A1c by 6 months postindex visit (accounting for whether BP data were taken in person or reported by the patient); and (3) Change in CVD risk factors by end of follow-up period. To do so, we will conduct adjusted regression analyses using longitudinal electronic health record data.

- To assess action taken on needed care, data for each factor will be extracted at each
  visit in the study period. We will use adjusted logistic regression models, with a
  dichotomous outcome of action taken or not taken.
- To assess *impact on individual CVD risk factors*, data for each factor will be extracted at index visit and all visits in the follow-up period (coded as controlled vs. not).
- Generalized linear mixed models (GLMM) with time nested within patients will be used to determine if risk factor control differs across encounter types, to estimate the effect of encounter type on change over time in CVD risk score and BP and A1c control. All encounters for each eligible patient will be included. CVD risk is influenced by factors amenable to clinical intervention (e.g., BP) and others that are irreversible (age); absent intervention, overall risk should increase with age. These analyses will be adjusted for or stratified by potential confounders at the patient, provider, and encounter level. This will include accounting for whether post-index visit encounters were in-person or VC, and the reason for the encounter, as in-person encounters in the post-COVID period may be for different reasons than VC encounters.

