#### Statistical Power

To conservatively calculate power for our main outcome (CVD risk score) we estimated 60 clinics with >35 high-CVD risk patients, randomized to two arms; then, using means and standard deviations for this measure from previous studies, we varied effect size associated with the group x time interaction and intraclass correlation. We examined a 1.5%, 2%, 3% greater absolute reduction in risk score over time in intervention vs. control CHCs. Aggressive management can reduce 10-year CVD risk by an absolute 4-5% in high-risk patients in a short time. We do not expect so large an effect and have power to detect smaller effects. **Supplement Addendum (Aim 2b).** This is a 2x2 repeated measures design with two groups of subjects measured at two time points. The primary goal is to compare change across time in group 1 (inperson index encounters) to change across time in group 2 (VC index encounters). A conservative estimate (based on preliminary results from the parent study) of 6000 patients in group 1 and 6000 in group 2 achieve 100% power to detect a difference in mean changes in CVD risk score of 5.0, with a standard deviation of 9.1 at the first time point, a standard deviation of 9.1 at the second time point, and a correlation between measurement pairs of 0.200. The significance level (alpha) is 0.050 using a two-sided, two-sample t-test.

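### The Aim 2b mixed models name no clinic term, so the encounter-type contrast ignores clustering of change by clinic and could also pick up differences in trend between clinics

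*Combined protocol and SAP*

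**What the plan says.** The Regression Analyses (Aim 2b) part of the Supplement Addendum in Section 7.a specifies the model: "Generalized linear mixed models (GLMM) with time nested within patients will be used to determine if risk factor control differs across encounter types". Its purpose is "to estimate the effect of encounter type on change over time in CVD risk score and BP and A1c control". On adjustment it says: "These analyses will be adjusted for or stratified by potential confounders at the patient, provider, and encounter level". The same list opens with "Encounter is the unit of analysis".

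The supplement covariate table in Section 6.b has readable rows for patient, comorbidity, index-visit, post-index-encounter and provider factors. The provider row reads "Degree (MD, RN, PA, etc.); Prescribing privileges: YN; # in patient panel". No readable row is for clinic, whereas Table 6, for the parent trial, has a row for other clinic factors.

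Elsewhere in Section 7.a clinic is modelled. The Intent to Treat Analysis says that "clustering was accounted for by random effects for clinic and patient, and a fixed effect for organization", and explains that "much organization-level variance could be attributed to the clinic level". The Secondary Analyses use random effects for provider and clinic. The Statistical Power paragraph for Aim 2b describes the comparison ("The primary goal is to compare change across time in group 1", in-person index encounters, against virtual index encounters) and sizes it with a two-sample t-test on 6,000 patients per group, with no clustering term.

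**The concern.** Encounter type is not randomized, and patients at one clinic share its staff, workflows and scheduling. Two things can follow if clinic is left out.

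First, if clinics differ in how risk changes over time and also in how much of their care is virtual, patients are not independent for this contrast and the standard error is too small. This needs no systematic link between the two.

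Second, if clinics with more virtual care also have systematically different trends, part of that difference enters the encounter-type estimate as bias.

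The documents give some reason to expect clinic trends to differ: CV Wizard is activated clinic by clinic, with Arm 2 starting 18 months after Arm 1 (Section 4), and the Aim 1 power work considers arm differences of 1.5% to 3% in absolute risk reduction. At stake is whether the supplement credits or blames virtual care for differences that belong to clinics.

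**Working it through.** **The plan's own figure.** Inputs from Statistical Power, Aim 2b: 6,000 patients per group, SD 9.1 at each time point, correlation 0.200, difference 5.0, two-sided alpha 0.05.

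- SD of change = √(9.1² + 9.1² − 2 × 0.2 × 9.1²) = √132.5 = 11.51.
- SE of the difference = 11.51 × √(2/6000) = 0.210.
- z = 5.0/0.210 ≈ 23.8, so the stated 100% power reproduces.
- Difference detectable at 80% power = (1.960 + 0.842) × 0.210 = 0.59 points.

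The last figure matters here. With so small a standard error, modest differences between clinics can reach significance.

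**Standard error without a clinic term.** Assumptions: 60 clinics (the figure in the Aim 1 power paragraph, borrowed), hence m = 12,000/60 = 200 patients each; mean virtual share 0.5; SD of clinic virtual share s = 0.1, 0.2 or 0.3; clinic ICC of change 0.005, 0.02 or 0.05; no link between clinic trend and virtual share.

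- Fraction of exposure variance lying between clinics: f = s²/(0.5 × 0.5) = 0.04, 0.16, 0.36.
- Variance inflation: D = 1 + (m − 1) × f × ICC.
- True rejection rate of a nominal 5% test: 2 × [1 − Φ(1.96/√D)].

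Example: D = 1 + 199 × 0.16 × 0.02 = 1.64, and 1.96/√1.64 = 1.53, giving about 12.6%.

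| ICC of change | s = 0.1 | s = 0.2 | s = 0.3 | Simulated, s = 0.1 to 0.3 |
|---|---|---|---|---|
| 0.005 | D 1.04, 5.5% | D 1.16, 6.9% | D 1.36, 9.3% | 4-8% |
| 0.02 | D 1.16, 6.9% | D 1.64, 12.6% | D 2.43, 20.9% | 7-19% |
| 0.05 | D 1.40, 9.7% | D 2.59, 22% | D 4.58, 36% | 9-36% |

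The simulated column comes from 1,500 null data sets per setting, with clinic share drawn from a Beta distribution and change regressed on encounter type. It agrees with the formula to within about 2 percentage points. With clinic fixed effects on change, rejection was 4-6% in every setting.

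The number of clinics matters. At ICC 0.02 with a quarter of exposure variance between clinics, the formula gives 25.7% for 30 clinics, 16.5% for 60 and 15.0% for 70.

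**If clinic trend is correlated with virtual share.** A second simulation (400 runs per setting, true effect zero, 60 × 200, s = 0.1-0.2, ICC 0.01-0.05) gave:

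| Correlation of trend with share | Mean estimate, no clinic term | p < 0.05, no clinic term | p < 0.05, clinic fixed effects on change |
|---|---|---|---|
| 0 | about 0 | 5-20% | 4-7% |
| 0.3 to 0.5 | 0.13 to 1.03 points | 11-97% | 4-7% |

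With clinic fixed effects on change the mean estimate stayed between −0.02 and 0.03. A clinic random effect on change, without a term for clinic virtual share, left 0.02 to 0.15 points of bias at correlations 0.3 to 0.5.

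**Precision given up.** A within-clinic contrast discards the fraction f of exposure variance, so the SE becomes about 0.210/√(1 − f): 0.214 at f = 0.04 and 0.263 at f = 0.36. The difference detectable at 80% power then runs from 0.60 to 0.74 points, against the 5.0 used for planning.

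**The case against.** The text does not say that clinic is excluded. Nesting time within patients may only describe the repeated measures, the provider level shows that the authors looked above the patient, and Section 9 leaves final analysis decisions until the variables have been examined. The supplement table is damaged after its independent-variables label, so a lost clinic row is possible. This stands as a caution about intent. It does not supply a clinic term: the running text lists the adjustment levels explicitly and clinic is not among them, while two other models in the same section name clinic. Provider degree, prescribing privileges and panel size do not stand in for it.

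A reader might infer that the plan will report clinic differences as an effect of virtual care. The documents do not support that. Bias needs clinic trends to be correlated with virtual-care share, and nothing in the documents measures that correlation. Without it, the harm is an understated standard error.

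The sizes are also assumed. At ICC 0.005 inflation is small, and the 36% needs both ICC 0.05 and a share SD of 0.3, where many clinics are nearly all virtual or all in person. The simulations compare unadjusted two-point changes in a continuous score. The planned models use all encounters with covariates, some of which may absorb clinic differences, and the BP and A1c control outcomes were not simulated. All of this stands, and it is why ranges are given.

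Finally, the Aim 1 and secondary models use clinic random effects, so asking only for clinic fixed effects by time would go beyond the plan's own practice. That is fair, and more than one form is acceptable.

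**Conclusion.** The concern holds in a limited form. The Aim 2b models as written name no clinic term, unlike the Aim 1 and secondary models, and following them would give standard errors for the encounter-type contrast that ignore clustering of change by clinic. The resulting type I error ranges from near nominal to about 36% over the assumed settings. Those rest on 60 equal clinics, a mean virtual share of 0.5, and ICC and share-spread values that the documents do not give. Bias in the estimate is a further, conditional risk.

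A reader might also infer that the 100% power claim fails. It does not: even with a design effect of 20.9 (60 clinics, ICC 0.10, encounter type varying only between clinics) power for 5.0 points stays at or above 99.9%, and the worst case examined, 30 clinics, gives 96%. The issue is validity of inference, not sample size. Aim 2b is an observational comparison, so the randomized Aim 1 result is untouched.

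**What to change.** In the Aim 2b regression text of Section 7.a, add clinic to the confounder levels and state that patients are nested in clinics with clinic-specific time trends. Either of two forms will do:

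- clinic fixed effects interacted with time; or
- random clinic intercepts and time slopes, plus each clinic's virtual-care share and its interaction with time.

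In both, the encounter-type by time estimate becomes a within-clinic contrast, and its standard error should reflect clustering by clinic. Copying the Aim 1 clinic random intercept alone would not be enough, because the estimand is change and an intercept does not absorb differences in trend.

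The cost is SAP wording, a larger model, and the loss of between-clinic exposure variation: about 4% to 36% of exposure variance for a share SD of 0.1 to 0.3. With about 12,000 patients that is affordable.

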- To assess whether CV Wizard moderated the relationship between encounter type and CVD outcomes, we will also conduct these analyses using only encounters where CV Wizard alerted the user that there are CDS suggestions. We will compare outcomes between encounters where CV Wizard was used (viewed or printed out) vs. not used, by including its use as a variable in the models described above.
   Data on race / ethnicity and gender will be obtained for all study patients; analyses will adjust or stratify for them as indicated.

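### Supplement Aim 2b: no encounter type × tool use term is stated for the moderation question, and no handling of clustering is stated for the repeated-encounter care-action model

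*Combined protocol and SAP*

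**What the plan says.** All of this is in section 7.a, Supplement Addendum, Regression Analyses (Aim 2b), unless another place is named.

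**Moderation.** The purpose is given as "To assess whether CV Wizard moderated the relationship between encounter type and CVD outcomes". The models are to be rerun "using only encounters where CV Wizard alerted the user that there are CDS suggestions", and encounters where the tool was viewed or printed are then compared with the rest: "vs. not used, by including its use as a variable in the models described above". No product of encounter type and use is mentioned, nor any comparison of the encounter-type effect between levels of use.

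**Care action.** The section opens with "Encounter is the unit of analysis". It continues "To assess action taken on needed care, data for each factor will be extracted at each" visit of the study period, so one patient can supply several records. For the yes/no outcome, "We will use adjusted logistic regression models"; nothing is said about correlation between records. The Supplement Addendum table in section 6.b lists needed care within 7 days under primary outcomes.

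**Other outcomes.** Risk score, BP and A1c control have their own bullet: "Generalized linear mixed models (GLMM) with time nested within patients". That bullet also provides for adjustment or stratification by confounders at patient, provider and encounter level. It states no provider or clinic random effect and no robust variance.

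**Parent study.** The Intent to Treat section names clinic and patient random effects, and Secondary Analyses names provider and clinic random effects. Both describe parent-study analyses.

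The "Independent vars" row of the supplement table lost its content in text extraction and could not be checked. The point therefore concerns the analysis text only.

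**The concern.** Moderation means that the in-person versus virtual difference depends on whether the tool was used. Restricting to alerted encounters changes the population. Entering use as a variable gives an average used-versus-unused difference. Neither step estimates how the encounter-type effect varies with use. An analyst who followed the text literally could report the use coefficient as the answer on moderation, or could choose an interaction after seeing the data.

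For care action, records from one patient, provider or clinic are likely to be correlated. A logistic regression that treats them as independent gives wrong intervals for the encounter-type effect. The sign of the error depends on how encounter type is spread within patients. The supplement's own table expects all-in-person, all-virtual and mixed patients, so the net direction cannot be read off beforehand.

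**Working it through.** **1. The plan's own figure.** Inputs from Statistical Power, Supplement Addendum: 6000 per group, SD 9.1 at both times, correlation 0.200, difference 5.0, two-sided alpha 0.05.
- SD of change = 9.1 × √(2 × (1 − 0.2)) = 11.51.
- SE of the difference = 11.51 × √(2/6000) = 0.210.
- 5.0/0.210 is about 24 standard errors, so power is 100%, as stated.
- Difference detectable at 80% power = (1.96 + 0.84) × 0.210 = 0.59.

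This figure covers the encounter-type contrast only. It covers neither moderation nor care action.

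**2. Does a use main effect reveal moderation?** Take four equal-sized cells with invented mean changes and fit main effects for type and use.

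| In-person, no use | In-person, use | Virtual, no use | Virtual, use | True interaction | Fitted use coefficient |
|---|---|---|---|---|---|
| 0 | −1 | 0 | −1 | 0 | −1.0 |
| 0 | 0 | 0 | −2 | −2 | −1.0 |
| 0 | −2 | 0 | 0 | +2 | −1.0 |
| 0 | −3 | 0 | 1 | +4 | −1.0 |

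The use coefficient is the same throughout. A binary illustration behaves alike. At 50% virtual and 20% use, cell probabilities 0.40, 0.50, 0.30, 0.40 (no moderation of the risk difference) give a use OR of 1.53. Probabilities 0.45, 0.45, 0.25, 0.45 (encounter-type OR 0.41 without use, 1.00 with use) give 1.54.

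**3. Precision of the interaction.** With use share p, assumed equal in both groups, SE = 0.210/√(p(1 − p)).
- p = 0.5: SE 0.420, detectable 1.18.
- p = 0.2: SE 0.525, detectable 1.47.
- p = 0.1: SE 0.701, detectable 1.96.

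This treats use as fixed per patient, although it varies by encounter. It is before clustering. The alert restriction multiplies it by 1/√(share of patients retained).

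**4. Ignoring patient clustering in the care-action model.** The documents give no ICC, encounter count or mix of types, so these are assumptions: latent ICC 0.1 and 0.3 (0.076 and 0.217 on the observed scale at a base probability of 0.40) and m = 2 to 6 encounters per patient. Variance inflation is V = 1 + (m − 1) × ρx × ρy, where ρx is the within-patient correlation of encounter type and ρy that of the outcome. Type I error is 2 × (1 − Φ(1.96/√V)).

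| Encounter type within patient | ρx | V, lowest to highest | Type I error |
|---|---|---|---|
| Balanced mix | −1/(m − 1) | 0.783 to 0.924 | 2.7–4.1% |
| Varies freely | 0 | 1 | 5.0% |
| Half of patients one type only | 0.5 | 1.038 to 1.542 | 5.4–11.5% |
| Constant | 1 | 1.076 to 2.085 | 5.9–17.5% |

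With only 2–3 encounters, the last two rows become 5.4–7.6% and 5.9–10.2%.

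Simulation (1500 patients, 4 or 6 encounters, 8000 datasets per setting) gave 2.8–4.5%, 4.3–5.4%, 5.7–11.3% and 7.3–17.5% for the four rows. Patient-cluster-robust errors gave 4.3–5.6% throughout.

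**5. Provider level.** With 120 providers, 100 encounters each and ICC 0.02–0.05, simulated type I error was about 5% when virtual shares varied between providers with SD 0–5 points, and 6.5–8.7% at SD 15 points. Clinic level was not quantified.

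**The case against.** The best reply is that both gaps are silences in a short plan. Including use as a variable, under a stated moderation purpose, does not rule out a product term, and a competent analyst might fit one. Adjusted logistic regression does not say that records will be treated as independent. Aim 2b is described as using longitudinal data, the parent-study analyses use multilevel models, and section 9 leaves final analysis decisions until distributions have been examined. All of this stands. It makes a naive analysis less likely, but the moderation test and the variance method remain unstated.

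Four stronger readings are tempting, and the documents do not support them.
- A reader might infer that the plan commits to a model that cannot address moderation. It only fails to state the term, and the lost table row might bear on this.
- A reader might infer that provider factors are ignored in the GLMM. Provider-level confounders are named for adjustment; what is missing is a random effect or robust variance.
- A reader might take 17.5% as the expected error rate. It needs six encounters, ICC 0.3 and one encounter type per patient, whereas the plan expects some mixed patients. Only encounters with needed care enter this outcome, so fewer records per patient are plausible.
- A reader might extend the point to the trial's main result. Aim 1 uses separate models with their own random effects.

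The binary example in step 2 uses invented cells and has no time term. Its no-moderation case is null for the risk difference, while its interaction OR is 0.667/0.643 = 1.04. It is illustrative only; the argument rests on a main effect not being an interaction.

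**Conclusion.** The point holds as two omissions in the analysis text of the observational supplement.

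(a) The only stated modelling step for the moderation question yields a use main effect, which does not answer that question. This needs no numerical assumption.

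(b) The care-action model, for a supplement primary outcome, has repeated encounters and no stated variance method. Under the assumed inputs in step 4, ignoring patient clustering gives type I error of about 3–4%, 5%, 5–12% or 6–18%, depending on how encounter type varies within patients. The intervals could be too wide, about right or too narrow. The GLMM handles repeated times within patient but leaves provider and clinic correlation unstated.

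Part (b) carries more weight because of the outcome's primary status; part (a) concerns an additional analysis. The plan should be amended on both, with medium confidence given the lost table row. The 100% power figure reproduces.

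**What to change.** **Moderation.** In the alert-only models add encounter type × CV Wizard use, and its product with time in the change models. Name this as the moderation test. Report the encounter-type effect with its interval at each level of use.

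**Clustering.** Fit the care-action model with a patient random effect plus a clinic or provider term, or use cluster-robust errors by clinic. State the clinic or provider clustering term for the GLMM. Report how much encounter type varies within patient and within provider, so that readers can see which row of the step 4 table applies.

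**Cost.** One sentence each in the plan, plus model code; no new data. Intervals may widen or narrow. The main drawback is the low precision of the interaction (step 3), although the detectable values there remain below the 5.0 points used in the plan's power statement. A null moderation result should be read with its interval.
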